8.2.2 Vital Signs

Vital signs to be collected as outlined in the SoA (Table 1-1) and include body temperature, heart rate, blood pressure, and respiratory rate.

Body temperature will be assessed per the local practice (temporal or otic are preferred sites), and site will be recorded. Pulse rate, respiratory rate, and blood pressure will also be assessed per site SOC. Where possible the same methods should be used throughout the study for an individual participant.

Blood pressure and pulse measurements should be preceded by at least 5 minutes of rest for the participant in a quiet setting without distractions (e.g., television, cell phones). During study intervention administration, an alarm threshold should be set for heart rate at 120 beats/min (or as indicated by the Investigator), as outlined in the SoA (Table 1-1).

Vital signs (to be taken before blood collection for laboratory tests) will be measured after the participant has been sitting for 5 minutes.

8.2.3 Electrocardiograms

Single 12-lead ECG will be obtained as outlined in the SoA (Table 1-1) using an ECG machine that automatically calculates the heart rate and measures PR, QRS, QT, and QTcF intervals for local reading.

8.2.4 Clinical Safety Laboratory Assessments

Refer to Appendix 3 for the list of clinical laboratory tests to be performed and to the SoA (Table 1-1) for the timing and frequency.

The Investigator must review the laboratory report, document this review, and record any clinically relevant changes occurring during the study in the AE section of the CRF. The laboratory reports must be filed with the source documents. Clinically relevant abnormal laboratory findings are those which are not associated with the underlying disease, unless judged by the Investigator to be more severe than expected for the participant's condition.

All laboratory tests with values considered clinically abnormal during participation in the study or within 4 days after the last dose of study intervention should be repeated until the values return to normal or baseline or are no longer considered clinically significant by the Investigator or Medical Monitor.

- If such values do not return to normal/baseline within a period of time judged reasonable by the Investigator, the etiology should be identified, where possible, and the Sponsor notified.
- All protocol-required laboratory assessments, as defined in Appendix 3, must be conducted in accordance with the Laboratory Manual and the SoA (Table 1-1).
- If laboratory values from laboratory assessments not specified in the protocol and performed at the institution's local laboratory result in the need for a change in participant management or are considered clinically relevant by the Investigator (e.g., are considered to be an SAE or an AE), then the results must be recorded in the CRF.

8.3 Adverse Events and Serious Adverse Events

The definitions of AEs and SAEs can be found in Appendix 4.

Adverse events will be reported by the participant (or, when appropriate, by a caregiver, surrogate, or the participant's legally authorized representative).

The Investigator and any qualified designees are responsible for detecting, documenting, and reporting events that meet the definition of an AE or SAE and remain responsible for following

up AEs that are serious, considered related to the study intervention or the study, or that caused the participant to discontinue the study intervention (see Section 7).

8.3.1 Time Period and Frequency for Collecting AE and SAE Information

All AEs and SAEs will be collected from signing of informed consent until the last follow-up visit at the time points specified in the SoA (Table 1-1).

All SAEs will be recorded and reported to the Sponsor or designee within 24 hours of the Investigator becoming aware of the SAE, as indicated in Appendix 4. The Investigator will submit any updated SAE data to the Sponsor within 24 hours of it being available.

Investigators are not obliged to actively seek AEs or SAEs after the conclusion of study participation. However, if the Investigator learns of any SAE, including a death, at any time after a participant has been discharged from the study, and he/she considers the event to be reasonably related to the study intervention or study participation, the Investigator must promptly notify the Sponsor.

8.3.2 Method of Detecting AEs and SAEs

The method of recording, evaluating, and assessing causality of AEs and SAEs and the procedures for completing and transmitting SAE reports are provided in Appendix 4.

Care will be taken not to introduce bias when detecting AEs and/or SAEs. Open-ended and non-leading verbal questioning of the participant is the preferred method to inquire about AE occurrence.

8.3.3 Follow-up of AEs and SAEs

After the initial AE/SAE report, the Investigator is required to proactively follow each participant at subsequent visits/contacts. All SAEs will be followed until resolution, stabilization, until the event is otherwise explained, or the participant is lost to follow-up (as defined in Section 7.4). Further information on follow-up procedures is given in Appendix 4.

8.3.4 Regulatory Reporting Requirements for SAE

Prompt notification (within 24 hours, see Appendix 4) by the Investigator to the Sponsor of an SAE is essential so that legal obligations and ethical responsibilities towards the safety of participants and the safety of a study intervention under clinical investigation are met.

The Sponsor has a legal responsibility to notify both the local regulatory authority and other regulatory agencies about the safety of a study intervention under clinical investigation. The Sponsor will comply with country-specific regulatory requirements relating to safety reporting to the regulatory authority, Institutional Review Board (IRB)/Independent Ethics Committee (IEC), and Investigators.

Investigator safety reports must be prepared for suspected unexpected serious adverse reactions (SUSARs) according to local regulatory requirements and Sponsor policy and forwarded to Investigators as necessary.

An Investigator who receives an Investigator safety report describing an SAE or other specific safety information (e.g., summary or listing of SAE) from the Sponsor will file it along with the Investigator's Brochure and will notify the IRB/IEC, if appropriate according to local requirements.

8.3.5 Pregnancy

All women, including women of childbearing potential are allowed in the study. Urine pregnancy test will be performed on female participants of childbearing potential and pregnant females at screening. Females who are not of child bearing potential do not need to undergo a screening pregnancy test.

Pregnant females will be followed to determine the outcome of the pregnancy:

- The Investigator will collect any follow-up information on the participant and the neonate and the information will be forwarded to the Sponsor. Generally, follow-up will not be required for longer than 6 to 8 weeks beyond the estimated delivery date. Any termination of the pregnancy will be reported, regardless of fetal state (presence or absence of anomalies) or indication for the procedure.
- While pregnancy itself is not considered to be an AE or SAE, any pregnancy complication or elective termination of a pregnancy will be reported as an AE or SAE. Abnormal pregnancy outcomes (e.g., spontaneous abortion, fetal death, stillbirth, congenital anomalies, ectopic pregnancy) are considered to be SAEs. Any post-study pregnancy-related SAE considered reasonably related to study intervention by the Investigator will be reported to the Sponsor as described in Section 8.3.4. While the Investigator is not obligated to actively seek this information in former study participants, he or she may learn of an SAE through spontaneous reporting.

8.3.6 Disease-Related Events and/or Disease-Related Outcomes Not Qualifying as AEs or SAEs

The following disease-related events (DREs) are common in participants with COVID-19 and can be serious/life-threatening:

- Fever
- Cough*
- Dyspnea*
- Asthenia
- Loss of sense of taste and smell

**A cough or dyspnea episode related to study intervention administration does not meet the definition of a DRE and should be reported as an AE.*

Because these events are typically associated with the disease under study, they will not be reported as AEs.

NOTE: However, if either of the following conditions applies, then the event must be recorded and reported as an SAE (instead of a DRE):

- The event is, in the Investigator's opinion, of greater intensity, frequency, or duration than expected for the individual participant.

OR

- The Investigator considers that there is a reasonable possibility that the event was related to study intervention.

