4.1 Overall Design

This is an open-label, randomized, multicenter, parallel group, concurrent, controlled study in hospitalized participants with COVID-19 requiring supplemental oxygen (WHO ordinary scale level 4) using a sequential adaptive design to evaluate the efficacy and safety of RESP301 added to standard of care (SOC). Approximately 300 adult (male and female) participants will be consented and randomized 2:1 to the Investigational arm or the Control arm. Participants randomized to the Investigational arm will receive inhaled RESP301 (6 mL) administered using a vibrating mesh nebulizer TID for up to 10 days in addition to the standard of care (SOC) while participants in the Control arm will receive SOC alone.

The study will be divided into the following periods:

- Screening period: starts up to 2 days (48 hours) prior to and extends up to the day of treatment initiation (Day 1); Days -2, -1 and 1
- Intervention period: up to 10 days; Day 1 to Day 10
- Efficacy follow-up: Day 14 and Day 28 (± 2 days)
- Safety follow-up: 28 days after treatment initiation; with the participant being contacted by phone call, if not still hospitalized, on Day 28 (± 2 days)

After screening, eligible participants will be randomized to either RESP301+SOC or SOC alone on Day 1, and the study treatment will be initiated as applicable (Table 1-1). Screening and randomization may happen on the same day (Day 1).

An individual administration of study intervention will be stopped, and supplemental oxygen resumed, if threshold limits of SpO₂ 89% or heart rate 120 beats/min (or as indicated by the Investigator) are exceeded (see Section 4.2 and Section 8.1.2). However, the participant may continue with subsequent doses if the Investigator judges that the benefit / risk ratio remains positive. In this case, the instruction to continue should be duly recorded in the participant's hospital file and the subsequent nebulization should be closely monitored. Inhalation of study intervention should be completed within 20 minutes. A staggered dosing approach will be used for the first 10 participants (up to the first Independent Data Monitoring Committee [IDMC] safety review) to monitor tolerability and response to RESP301 (see Sections 6.1 and 9.6).

The study treatment will be permanently discontinued prior to 10 days if the participant:

- Improves to level 1 or 2 of the modified WHO ordinal scale;
- Progresses to a level > 4 of the modified WHO ordinal scale;

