10.4.2 Definition of SAE

If an event is not an AE per definition above, then it cannot be an SAE even if serious conditions are met (e.g., hospitalization for signs/symptoms of the disease under study, death due to progression of disease).

An SAE is defined as any untoward medical occurrence that, at any dose:

a. Results in death

b. Is life-threatening

The term 'life-threatening' in the definition of 'serious' refers to an event in which the participant was at risk of death at the time of the event. It does not refer to an event, which hypothetically might have caused death, if it were more severe.

c. Requires inpatient hospitalization or prolongation of existing hospitalization (Applies only during the safety follow up period for participants who may have been discharged during the treatment period, ie, between Day 1 and Day 10)

- In general, hospitalization signifies that the participant has been detained (usually involving at least an overnight stay) at the hospital or emergency ward for observation and/or intervention that would not have been appropriate in the physician's office or outpatient setting. Complications that occur during hospitalization are considered AEs. If a complication prolongs hospitalization or fulfills any other serious criteria, the event is serious. When in doubt as to whether "hospitalization" occurred or was necessary, the AE should be considered serious.
- Hospitalization for elective intervention of a pre-existing condition that did not worsen from baseline is not considered an AE.

d. Results in persistent disability/incapacity

- The term disability means a substantial disruption of a person's ability to conduct normal life functions.
- This definition is not intended to include experiences of relatively minor medical significance such as uncomplicated headache, nausea, vomiting, diarrhea, influenza, and accidental trauma (e.g., sprained ankle) which may interfere with or prevent everyday life functions but do not constitute a substantial disruption.

e. Is a congenital anomaly/birth defect

f. Other situations

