10.4.3 Recording and Follow-up of AE and SAE

AE and SAE Recording

When an AE/SAE occurs, it is the responsibility of the Investigator to review all documentation (e.g., hospital progress notes, laboratory, and diagnostics reports) related to the event.The Investigator will then record all relevant AE/SAE information in the CRF.It is not acceptable for the Investigator to send photocopies of the participant's medical records to the clinical research organization (CRO) in lieu of completion of the AE/SAE CRF page.There may be instances when copies of medical records for certain cases are requested by the CRO. In this case, all participant identifiers, with the exception of the participant number, will be blinded on the copies of the medical records before submission to Parexel Safety Services for review.The Investigator will attempt to establish a diagnosis of the event based on signs, symptoms, and/or other clinical information. In such cases, the diagnosis (not the individual signs/symptoms) will be documented as the AE/SAE.
Assessment of Intensity

The Investigator will make an assessment of intensity for each AE and SAE reported during the study and assign it to one of the following categories:
 
Mild: An event that is easily tolerated by the participant, causing minimal discomfort and not interfering with everyday activities.Moderate: An event that causes sufficient discomfort and interferes with normal everyday activities.Severe: An event that prevents normal everyday activities. An AE that is assessed as severe should not be confused with an SAE. Severe is a category utilized for rating the intensity of an event; and both AE and SAE can be assessed as severe. 
An event is defined as 'serious' when it meets at least one of the predefined outcomes as described in the definition of an SAE, NOT when it is rated as severe.

Assessment of Causality

- The Investigator is obligated to assess the relationship between study intervention and each occurrence of each AE/SAE.
- A "reasonable possibility" of a relationship conveys that there are facts, evidence, and/or arguments to suggest a causal relationship, rather than a relationship cannot be ruled out.
- The Investigator will use clinical judgment to determine the relationship.

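### The NOTE in section 8.3.6 turns disease-related events into SAEs without any seriousness criterion, against Appendix 4 and, for cough and dyspnea, against its own footnote

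*Protocol*

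**What the plan says.** Section 8.3.6 (version 2.0) names five disease-related events (DREs): fever, cough, dyspnea, asthenia, and loss of taste and smell. They are exempt from AE reporting. Two further statements qualify the exemption.

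- A footnote to cough and dyspnea says that an episode "related to study intervention administration does not meet the definition of a DRE and should be reported as an AE".
- A NOTE says that if either of two conditions applies, "then the event must be recorded and reported as an SAE (instead of a DRE". The first condition is that the event is "of greater intensity, frequency, or duration than expected for the individual participant". The second is: "The Investigator considers that there is a reasonable possibility that the event was related to study intervention".

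Appendix 4 sets the general rule. Section 10.4.2 begins "An SAE is defined as any untoward medical occurrence that, at any dose" and continues with a list of outcomes, a to f: death, threat to life, hospitalization, disability, congenital anomaly, and other important medical situations. Section 10.4.3 adds that an event is serious when "it meets at least one of the predefined outcomes as described in the definition of an SAE", and not because it is rated severe. Section 10.4.1 keeps signs of the studied disease out of the AE definition unless they are more severe than expected.

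The number and cumulative incidence of SAEs are a safety endpoint (section 3). SAEs and related SAEs are to be tabulated (section 9.4.5.1), and the IDMC assesses safety at each interim analysis (section 9.2).

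**The concern.** A mild cough after nebulization, judged related, is an AE under the footnote and an SAE under the NOTE a few lines later. A related but non-serious fever is an SAE under the NOTE with nothing in the section to say otherwise. In both cases Appendix 4 would call the event an AE.

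What is at stake is how the SAE comparison reads. In section 4.1, "participants in the Control arm will receive SOC alone", so no control participant can have an event related to RESP301 or its nebulization. SAEs created by relatedness alone therefore fall on one side. Sites that resolve the contradiction differently will also report the same event differently. The IDMC looks at safety early, after 10 and 20 participants, when a few misclassified events would weigh heavily. The primary efficacy test is not affected.

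**Working it through.** **Step 1. Compare the instructions for each kind of non-serious event.**

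| Non-serious event | Footnote, 8.3.6 | NOTE, 8.3.6 | Appendix 4 |
|---|---|---|---|
| Cough or dyspnea related to administration | AE | SAE | AE: no listed outcome |
| Fever, asthenia, loss of taste or smell, possibly related | silent | SAE | AE: relatedness is not a criterion |
| Any listed event worse than expected | silent | SAE | AE: 10.4.1 brings it within the AE definition; 10.4.3 separates severe from serious |

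The NOTE disagrees with Appendix 4 in all three rows. It disagrees with its own footnote in the first. For fever, asthenia and loss of taste or smell judged related, no competing text in the section softens it.

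**Step 2. Which arm is affected.** Relatedness can arise only with RESP301. Being worse than expected can be judged in either arm.

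**Step 3. Size, for the relatedness condition only.** The protocol states neither an expected SAE rate nor a rate of related cough, dyspnea or other listed events, so there is no figure to reproduce. An illustration needs two assumptions:

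- s = proportion with a true SAE, the same in both arms (assumed 10%, 20% or 30%);
- r = proportion of RESP301 participants with a non-serious related listed event, independent of s (assumed 2% to 20%).

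Reported SAE proportion in RESP301 = s + (1 − s) × r. In control it stays at s. Participants added = 200 × (1 − s) × r, with the planned arm sizes of 200 and 100 (section 9.2).

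Example: s = 20%, r = 10% gives 0.20 + 0.80 × 0.10 = 0.28, and 200 × 0.80 × 0.10 = 16 added participants.

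| s (both arms) | r = 2% | r = 5% | r = 10% | r = 20% |
|---|---|---|---|---|
| 10% | 11.8% (ratio 1.18) | 14.5% (1.45) | 19.0% (1.90) | 28.0% (2.80) |
| 20% | 21.6% (1.08) | 24.0% (1.20) | 28.0% (1.40) | 36.0% (1.80) |
| 30% | 31.4% (1.05) | 33.5% (1.12) | 37.0% (1.23) | 44.0% (1.47) |

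Cells show the reported RESP301 incidence and its ratio to control. At s = 20% the added participants number about 3, 8, 16 and 32 of 200. With the NOTE corrected, the artificial excess is zero in every cell.

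**The case against.** The best defence is that the footnote is the more specific rule. An administration-related cough or dyspnea "does not meet the definition of a DRE and should be reported as an AE", so it has left the DRE category before the NOTE applies. The amendment history supports this as the intent: version 1.0 attached the footnote marker to dyspnea only, and version 2.0 added it to cough. This stands in part. A reader might infer that every treatment-related cough must be reported as an SAE; the text supports only that sites have two conflicting instructions. The defence does not reach fever, asthenia or loss of taste and smell, nor the worse-than-expected condition.

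A second defence is that the NOTE was meant only for DREs that are already serious, since the section opens by saying these events can be. The text does not say so. The preceding sentence exempts all the listed events, serious or not, and the NOTE refers back to that same set. Criterion f in section 10.4.2 leaves room for judgement, but only for events that may jeopardize the participant or need intervention to avert a listed outcome. The NOTE makes no reference to it.

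Third, there are checks downstream. Under section 10.4.4 the sponsor side evaluates the seriousness, causality and expectedness of each report, and expedited notice to authorities needs a serious, associated and unexpected event. A reader might infer that non-serious events would go to regulators as expedited reports; the protocol does not support that. What does increase is 24-hour reporting from site to sponsor. Section 10.4.3 also asks for positive grounds before a reasonable possibility is recorded, which limits how often the condition is met. Tabulation by preferred term would let the IDMC notice a cluster of cough reports.

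Fourth, section 2.2.1 presents cough or bronchospasm from mannitol as a potential effect in susceptible individuals, and section 7.1 calls bronchospasm a theoretical risk at these concentrations. The protocol foresees these events but does not predict that they will be common.

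**Conclusion.** The point holds as an internal contradiction: the NOTE assigns SAE status without a seriousness criterion, against sections 10.4.1 to 10.4.3 and, for administration-related cough and dyspnea, against the footnote. Followed as written, it puts non-serious events into a stated safety endpoint.

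The size is not known. Under the assumptions shown (20% true SAEs in each arm, 2% to 20% with a non-serious related event, independence between the two), reported incidence is about 22% to 36% in RESP301 against 20% in control. If sites follow the footnote for cough and dyspnea, r shrinks to the other listed events.

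Two stronger readings are not supported. One is that the distortion is confined to RESP301: that is true of the relatedness condition, not of the worse-than-expected condition. The other is that the excess in percentage points equals the rate of related events: that would need no affected participant also to have a true SAE, and the protocol gives no rate to start from.

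The text examined is that of version 2.0. Section 8.3.6 of Amendment 2 (version 3.0) is not in the supplied document; its change table lists no change there, so carry-over is likely but not shown. The correction should be made, but it concerns descriptive safety reporting only.

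**What to change.** Reword the NOTE so that a listed event meeting either condition is recorded as an AE instead of a DRE, and as an SAE only if it also meets a seriousness criterion in section 10.4.2. This brings the NOTE, the footnote and Appendix 4 into line. First confirm that version 3.0 still carries the same NOTE.

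The cost is one sentence in section 8.3.6 and the matching line in site training. If participants have already been enrolled under the existing wording, SAEs from the listed terms should be checked against section 10.4.2 before the next IDMC review.
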